2.3 Effect of Antibacterial Home Cleaning and Hand Washing Products on Infectious Disease

Symptoms:⁵⁵ [name] conducted ARI/ILI surveillance in households using weekly telephone reporting. Research staff determined the sensitivity (93%) and specificity (97%) of the first 100 self-reports of symptoms through an in-person assessment conducted during a home visit. During 26.2%, 23.3% and 10.2% of household-months at least one household member had a runny nose, cough, and/or sore throat.

2.4 Impact of Non-Pharmaceutical Interventions on URIs and Influenza in Households:²⁹ [name] and colleagues used twice weekly structured, automated telephone messages using a toll-free number to detect symptoms of ARI/ILI in household members. There were 5,034 ARIs reported, of which 669 cases were consistent with ILI and 78 (11%) were laboratory-confirmed cases of influenza.

2.5 Text Messaging and Vaccine Safety Surveillance:⁶²⁻⁶⁴ Drs. [name] and [name] have also successfully demonstrated text message vaccine adverse event surveillance in pediatric and obstetric patients.

3. Identifying Etiology of ARI/ILI

3.1 MoSAIC: MOBILE Surveillance for ARI/ILI in the Community:¹⁸ In this study, 59.5% of 1677 samples were positive for a respiratory pathogen; 21.4% of positive samples collected November-March were positive for influenza. In addition, 14 other respiratory pathogens were detected including subspecies of coronavirus and parainfluenza, respiratory syncytial virus (RSV), adenovirus, human metapneumovirus (hMPV), rhinovirus/enterovirus (RV/EV), *Chlamydophila pneumoniae* and *Mycoplasma pneumoniae*.

3.2 Impact of Non-Pharmaceutical Interventions on URIs and Influenza in Crowded, Urban Households:²⁹

33.3% of deep nasal swabs obtained were positive for influenza of which 43.6% were influenza A and 56.4% were influenza B. Among the 66.7% of swabs that tested negative for influenza, 30.8% were positive for other viruses including RSV, parainfluenza, RV/EV, adenovirus, and hMPV.

3.3 Viral surveillance: As a member of the NewYork-Presbyterian Hospital Department of Infection Prevention and Control and the hospital epidemiologist at Morgan Stanley Children's Hospital, [name] has helped to craft interventional strategies to prevent transmission of respiratory pathogens in healthcare settings which include tracking and trending community-onset and healthcare-associated respiratory viral pathogens.

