identify reasons for not reporting, and to update contact information including any new number to be used. Based on our previous work, we expect to contact less than 20 (5%) households monthly. Similar to our previous studies, a payment of \$15/month will be provided to household reporters who respond to $\geq 75\%$ of the text messages during the previous month (i.e., at least 9 text messages/month) to defray the costs of the required text messages. The payment will be made remotely via a refillable cash card.

Confirmation of ARI/ILI Symptoms via Phone Calls. Any *research staff or HH-generated message* indicating illness in a household member will trigger an automatic email notifying research staff. Staff will immediately contact (within 2-4 hours) the household reporter to confirm ARI/ILI symptoms. The use of text messaging to perform the first level of surveillance allows staff to focus on households with ill participants, which we expect to be about 5-15 households at any given reporting day. In the MoSAIC study, we successfully contacted all families within 12 hours of reporting via text message, 7 days a week. Symptoms will be confirmed over the phone using the Symptoms Reporting Form used in previous studies^{18,29,54,69} (Appendix).^{18,29} Anyone meeting case definition for ARI or ILI will be swabbed. The CDC-provided case definition for ARI is presence of at least two of the following: (1) rhinorrhea/nasal congestion; (2) sore throat; (3) cough; (4) fever/feverishness; (5) myalgia. The ILI definition is at least two of the following signs and symptoms: fever, cough, headache, sore throat, or myalgia.¹⁶ In addition, for those <1 years-old, a swab will be collected even if rhinorrhea is the only symptom; young children have viral illnesses that manifest differently than in adults.⁷⁰ We are using ARI and ILI criteria to collect swabs, since a poor correlation between CDC ILI definitions and influenza has been noted by ourselves and others.⁷¹

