
Blinding. Participants cannot be blinded as to which group they are randomized. Laboratory technicians ascertaining the primary endpoint will be blinded as to arm assignment, and the research staff will also be blinded as above. The data analysis will be blinded as to group assignment by using a dummy variable for intervention vs. comparison until the analyses are completed.

TEXT MESSAGE-BASED INTERVENTION

While **all** households will receive the surveillance text messages, we will randomize households within each surveillance community to **additionally** receive educational text message about ways to decrease household

transmission (surveillance + education arm) vs. standard care (surveillance-only arm). We will then assess the impact of the educational text messages primarily on secondary attack rates of influenza within households.

The comparison arm will not receive any educational text messages, only the surveillance ones as above.

Message Generation. When an ILI/ARI is reported, research staff will log it into the text message application. If the household is in the surveillance + education arm, the system will automatically send one educational message to the household reporter a day for three days; if it is surveillance-only the system will not send a message. This allows research staff to remain blinded. Messages will be based on whether it is an adult or child who is the index case (Appendix). We have chosen three messages since after that most within-household transmission will have occurred. The household reporter will be instructed on enrollment that they are to read the text message to the household members. We have designed 4 sets of message to be used in order per household i.e. each household will start with set one (see Appendix for adult and child-specific sets of messages). The message will be targeted to be from the recruitment site (e.g. doctor's office, Head Start). We will track reports of undelivered messages; these are visible in the text message application.

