All analyses will be based on randomized arm assignment (intention-to-treat). An ill person will be considered an ILI/ARI index case for a household if, at the onset of illness, no one else in the household had been symptomatic within the previous 5 days.²⁹ Non-index household members will be defined as secondary cases if they are confirmed by RT-PCR as influenza-positive on day 3 or day 5 swab (symptomatic or asymptomatic).¹⁶ Five days was selected based on our previous studies and the influenza incubation period.²⁹ The secondary attack rate will be defined as the number of secondary cases of laboratory-confirmed influenza (both symptomatic and asymptomatic) divided by the number of household members minus one (the index case). Secondary attack rates will be compared between the arms - surveillance plus education vs. surveillance-only - using chi square tests and a generalized linear mixed model (logistic regression for binary response, mixed model for clustering within a household). We will assess other co-variates in the models including for the index patient and household contacts: age, sex, vaccination status including vaccine type, antiviral use (treatment or prophylaxis), previous illness episodes reported for the household, influenza season and years in study.

Secondarily, we will assess the intervention's impact on additional outcomes using the same analyses as above: defining secondary cases based on (1) ILI-criteria (fever, cough, headache, sore throat, or myalgia) within 5 days of illness of index case; (2) ARI criteria (≥ 2 of a) rhinorrhea/nasal congestion; b) sore throat; c) cough; d) fever/feverishness; e) myalgia); (3) any laboratory-confirmed pathogen that is the same as the index case including non-influenza pathogens. An additional set of secondary outcome measures will be to assess the secondary attack rate at the household (cluster) level defined as the percentage of households with at least one secondary case as defined in the analyses above.

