We will use Pearson chi square to assess relationship between text message response rates and community, reporter's race/ethnicity, insurance and education. This will be defined as number of responses received per message sent. If more than one variable is significantly related to reporting rates ($p<0.1$), we will develop multivariable logistic models to assess this relationship. We will also assess response rates by arm.

SAMPLE SIZE AND POWER

We have based our sample size on the primary outcome. With 200 households per arm and an average of 3.8 persons/household, we will have 88% power to detect a decrease in secondary attack rates of laboratory-confirmed influenza from 12% (surveillance-only) to 5% (surveillance + education), based on type I error of 5% and an intracluster correlation coefficient of 0.29. The intracluster correlation, expected transmission rates for the surveillance-only arm, and effect size are derived from the paper by Cowling *et al.*, reporting a reduction from 12% to 5% between the hand hygiene and usual care arms in SAR when a non-text message based behavioral intervention was started at ≤ 36 hours of illness onset in the index case using laboratory-confirmed influenza as an outcome.¹⁶ In the MoSAIC study, secondary attack rates for laboratory-confirmed influenza have been 16.6% therefore an expected rate of 12% in the surveillance-only arm is conservative. We will also be powered for our secondary outcome; we will have 91% power to detect a decrease in symptomatic ILI/ARI from 23% to 11%.¹⁶ If we lose 80 households (20%) per season, we will still have at least 80% power to detect the decreases in both the primary and secondary outcome as above, even without household replacement.

POTENTIAL CHALLENGES AND SOLUTIONS Table 3

Challenge	Solution
1. Recruitment and retention	In our previous community studies retention was excellent. In our MoSAIC study, 75.9% of households recruited in year 1 were still in the study in year 3.
2. Non-representative sample	Since eligibility criteria include ≥ 3 members and ≥ 1 child, the sample will not be fully representative of the communities. However, the benefits of these inclusion criteria include higher likelihood of infection and transmission.
3. Reporting bias	3x/a week texting will decrease recall bias. We have shown under- and over-reporting to be low and confirmed the validity of household symptom self-reports.

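### The primary attack rate is analysed by assigned arm but only within episodes reported after randomisation, and the plan does not compare those episodes between arms

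*Combined protocol and SAP*

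**What the plan says.** All references are to the combined protocol and SAP. Households are randomised at enrolment (Randomization Procedures). The Statistical Plan, under the Aim, states "All analyses will be based on randomized arm assignment (intention-to-treat"). The same paragraph defines the unit that opens an analysed episode: "An ill person will be considered an ILI/ARI index case for a household if, at the onset of illness, no one else in the household"; the condition is that nobody else was symptomatic in the preceding five days. The SAR is the count of secondary laboratory-confirmed influenza cases "divided by the number of household members minus one (the index case"). The text does not say whether the index case must be influenza-positive.

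Episodes are found through household reports: "Any *research staff or HH-generated message* indicating illness in a household member will trigger an automatic email notifying research staff" (Confirmation of ARI/ILI Symptoms via Phone Calls). Under Blinding, "Participants cannot be blinded as to which group they are randomized". Under Message Generation, once an illness is logged in the education arm, "the system will automatically send one educational message to the household reporter a day for three days". Four message sets are prepared for successive use in a household, so repeat exposure is foreseen.

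The related checks are these:
- Text replies: "We will also assess response rates by arm" (Exploratory Aim), with the rate defined as replies per message sent.
- Missing data are classified by arm (Missing Data).
- Candidate covariates include age, sex, vaccination and antiviral use of index patients and contacts, and the household's earlier reported episodes (Aim).
- A secondary outcome gives the percentage of households with a secondary case, without saying which households form the denominator.

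**The concern.** Randomisation makes the two sets of households comparable. It does not by itself make the two sets of reported episodes comparable, because those arise later and depend on what households do. In the education arm, an episode after the first comes from a household that has already received messages about spread, severity and hygiene. Such a household might bring in fewer infections, or might report mild illness more or less readily.

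Two readings of the result are then at risk. A lower SAR could partly reflect a different mix of index episodes rather than less transmission. Conversely, if education prevents introductions, the SAR cannot show it, because a household with no reported episode adds nothing to numerator or denominator. As planned, the analysis would not let a reader tell these apart.

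**Working it through.** **The plan's own figure.** Sample Size and Power gives 88% power for 12% versus 5%, with 200 households per arm, 3.8 persons per household and an intracluster correlation of 0.29. Contacts per arm: 200 × 2.8 = 560. Design effect: 1 + (3.8 − 1) × 0.29 = 1.812. Effective n: 560/1.812 = 309. A two-sided 5% test of two proportions (two-sided assumed) then has 87.9% power. The figure reproduces. It treats every randomised household as supplying contacts, whereas the analysis can use only households with a reported episode.

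**How often education precedes an influenza episode.** Inputs:
- 5-15 ill households per reporting day (Confirmation of ARI/ILI Symptoms), out of 400.
- Three texts a week, November to March: 3 × 151/7 = about 65 reporting days per season.
- Three seasons (assumption; Table 4 gives surveillance in months 13-41, which fits if month 13 is November).
- Influenza share p = 0.595 × 0.214 = 12.7%. Preliminary Studies 3.1 reports 59.5% of samples positive for any pathogen, and "21.4% of positive samples collected November-March were positive for influenza". Applying 59.5% to November-March is an assumption.
- Episodes are Poisson with mean L per household, each is influenza independently with probability p, and one report equals one episode (assumptions).

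L per season = 5 × 64.7/400 = 0.81 to 15 × 64.7/400 = 2.43. Over three seasons it is 2.43 to 7.28.

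A household has at least one influenza episode with probability 1 − exp(−pL). Its very first episode is influenza with probability p(1 − exp(−L)). The share of first influenza episodes that follow an earlier episode is therefore 1 − p(1 − exp(−L))/(1 − exp(−pL)).

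| L | 1 − exp(−L) | 1 − exp(−pL) | Share after an earlier episode |
|---|---|---|---|
| 0.81 | 0.555 | 0.098 | 28% |
| 2.43 | 0.912 | 0.266 | 56% |
| 7.28 | 0.999 | 0.604 | 79% |

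This gives 28-56% in one season and 56-79% over three. If each episode produced two reports, L would halve and the ranges would be 16-37% and 37-67%.

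**What unequal reporting could do, with no true effect (assumed illustrations).** Suppose all reported episodes enter the denominator and non-influenza episodes give no influenza secondary cases. If the education arm reports non-influenza illness x times as often, the SAR ratio is 1/(p + (1 − p)x).
- x = 1.10: 1/1.087 = 0.92
- x = 1.25: 1/1.218 = 0.82
- x = 1.50: 1/1.436 = 0.70
- x = 0.75: 1/0.782 = 1.28, the opposite direction

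Suppose instead that only influenza-positive index episodes count, with half the households at a 20% attack rate and half at 4% (mean 12%). If high-transmission households in the education arm are 25% less likely to report, that arm's SAR is (0.375 × 20 + 0.5 × 4)/0.875 = 10.9%. If they are 50% less likely, it is (0.25 × 20 + 0.5 × 4)/0.75 = 9.3%.

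**Whether an existing check covers this.** A reply that nobody is ill counts as a response, and the monthly payment rewards replies, so equal reply rates can coexist with unequal illness reporting. The missing-data section is mainly concerned with contacts who do not swab; an illness never reported leaves no record to classify. Earlier reported episodes are themselves counted after randomisation, so adjusting for them does not restore comparability. None of these compares the number, severity or influenza positivity of index episodes by arm.

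**The case against.** The strongest reply is that any secondary attack rate must condition on an index case, the stated aim is transmission within households, and assigned arm is respected throughout. That stands. A reader might infer that the intention-to-treat principle is broken; the documents do not support this, since nobody is moved or excluded by what they received. Better behaviour in later episodes is also a legitimate effect of assignment, and preventing introductions is a different question from reducing transmission.

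Much of the process is shared. Swabbing, prompts, calls and payments are the same in both arms, staff confirming symptoms are blinded, and only the educational texts differ. A household's first episode is reported before any message, and nothing in the text shows that it has learned its arm by then. Table 3 claims low under- and over-reporting, and Preliminary Studies 2.3 gives 93% sensitivity and 97% specificity for self-reported symptoms. Those figures come from weekly telephone reporting in an earlier study and are not shown by arm, so they make a large reporting gap less likely without excluding a differential one.

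Two further inferences go too far. Because 12.7% of samples are influenza-positive, a reader might conclude that 1 − 0.127 = 87% of first influenza episodes follow education in that arm. That would need unlimited follow-up and is only an upper limit. A reader might also conclude that the plan makes no checks by arm; it makes some, but they address neighbouring questions. Finally, the planned 12% control rate fits influenza-positive index households better than all episodes, so the 0.92-0.70 illustration may not apply once the denominator is defined.

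**Conclusion.** The concern holds in limited form. The primary comparison is by assigned arm but conditional on an index episode that arises and is reported after randomisation by unblinded households, and the plan does not examine whether those episodes are comparable. Over three seasons, roughly 56-79% of first influenza episodes would follow an earlier one, which in the education arm means after at least one message set. In a single season it is 28-56%. These figures rest on the Poisson model, one report per episode and the assumed influenza share.

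The documents show that arm-dependent selection is possible, not that it occurs. Neither its direction nor its size can be derived from them, and the illustrations show only that moderate reporting differences would matter. This is an inexpensive improvement to the analysis plan, not a reason to reject the endpoint.

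**What to change.** Amend the Aim section of the Statistical Plan in four places.

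1. State that the SAR is compared by assigned arm but is conditional on a reported index episode, and say whether the denominator is limited to influenza-positive index episodes. State the denominator of the household-level secondary outcome too.
2. Pre-specify a comparison by arm, with estimates and confidence intervals, of confirmed ILI/ARI episodes and of influenza-positive index episodes per household-season, with index age and symptom count.
3. Add as a companion to the SAR the number of secondary laboratory-confirmed influenza cases per randomised household-season, from a count model clustered by household with an offset for member-weeks.
4. Add a sensitivity analysis limited to each household's first reported episode.

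Read the SAR alongside items 2-4. Do not make it depend on passing a comparability test: without a margin, a non-significant difference could pass for similarity, and a genuine fall in introductions could lead to a valid transmission effect being set aside.

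The cost is added wording and a few analyses of data already being collected. Item 3 is itself sensitive to under-reporting. Item 4 is less precise: on the three-season figures above, only 21-44% of first influenza episodes are also the household's first episode.

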In previous work, we demonstrated in one primarily Latino, urban sample, that text messaging by family members can be used to rapidly identify members with ILI/acute respiratory infections (ARI) early in an illness.¹⁸ This approach to early identification would enable implementation of an educational intervention targeted to the 36-hour timeframe. Providing education within a text message is a proven successful strategy to influence behavior.¹⁹⁻²² Using text message surveillance to trigger a novel educational intervention also allows inclusion of both medically and non-medically attended index cases, a key element in reducing influenza SAR since less than one-third of persons with laboratory-confirmed influenza seek medical care.¹⁸ Text messaging itself is scalable, low-cost, and can be used in low literacy populations.²³ However, using text-message based surveillance to trigger a real-time text-message behavioral educational intervention to decrease household influenza transmission has not been assessed. In evaluating the impact of this intervention strategy, the primary outcome will be laboratory-confirmed influenza. The primary outcome will be determined using self-swabs among household members to detect SAR, including asymptomatic infection and medically- and non-medically attended illness. We have successfully piloted self-swab collection.

Aim: To assess the impact of an educational intervention delivered by text messaging on transmission of influenza within households

Primary Outcome Hypothesis: Educational text-messages will reduce laboratory-confirmed influenza household transmission from 12% to 5%

Secondary Outcome Hypothesis: Educational text-messages will reduce ILI transmission from 23% to 11%

Exploratory Aim: To compare the yield of text message ILI/ARI surveillance among subgroups in a diverse, community sample

Hypothesis: Response rates to text messages will be similar among different sociodemographic groups.

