For the index case, we will ask that samples be obtained the same day as the report of illness to facilitate the yield of respiratory pathogens. We will then ask that everyone else in the household is swabbed 3 and 5 days after the onset of symptoms in the index case. We have chosen this timing, to maximize yield for influenza, since it has been estimated that the time between influenza infection in an index case and infection of secondary household contacts is 3.4 days [3.1, 3.7].^{7,10,13,24} It was also found that a single sample on day 4 or day 5 since the symptoms onset of the index case would have the most "detectable" infections circulating in households.²⁴ Households will be texted reminders on day 3 and 5 requesting that these samples be taken, and will be asked to text back confirmation. Households that do not text back confirmation will be called. We will ask that swabs be kept in their refrigerator, until mailing, as in our pilot study.

Once all samples are collected they will be placed in a pre-addressed, pre-stamped mailer and dropped into the regular mail, as in our pilot. They will be texted a final time on day 7 asking if swabs were sent back, and will be called if do not respond. An episode of ILI/ARI within a household will be considered completed when the last person within a household is symptom-free for 5 consecutive days; after that, new symptoms within a household would trigger consideration of a new ILI/ARI episode. As additional compensation for their time, households will receive \$5.00 when the swabs are received. We will track kits that are used, and a new kit will be mailed overnight when a household as used up all kits.

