to them. The coordinator will also ask about any problems or suggested changes. This process will be iterative until no new message changes are made. The translation process will be repeated with the final messages. We anticipate needing 40 households, 10 from each community, to pretest the messages. Households will receive a round-trip New York City subway Metrocard worth \$5.00 for participating in the pre-test.

DATA COLLECTION AND MANAGEMENT FOR BOTH ARMS

Survey Tools. Household and individual data will be gathered from the household reporter using two methods: a Demographic Survey adapted from previous studies^{18,29} and a Household Intake Form (Appendix). Surveys will be verbally administered by research staff at the baseline (enrollment) home visit in the reporter's preferred language, English or Spanish. We will obtain the following data at enrollment and update it annually:

- *Individual characteristics* (age, sex, race/ ethnicity, place of birth, length of time in U.S., preferred language, education, insurance, employment status, school/daycare, hours outside the home, general health status, presence of chronic respiratory disease or other illness, smoking/exposure to second-hand smoke).
- *Household characteristics* (composition, household density [ratio of people to bedrooms]).

Symptom Reports. We will call on day 10 after symptom onset of index case to assess ILI/ARI symptoms in household members, care sought, if anti-viral medication taken, and current influenza vaccination status (including type of vaccine) using the Follow-up form (Appendix).

Data Management. All data collection and storage will be HIPAA compliant as outlined in the Human Subjects Protection. [name] will supervise file cleaning and perform quality checks at least monthly. All study related documents and swab samples will contain a unique identifier for each participant.

STATISTICAL PLAN: Data analysis will be performed using SAS (Cary, NC).

AIM: To assess the impact of an educational intervention delivered by text messaging on transmission of influenza within households

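### The primary secondary attack rate, as written, does not require an influenza-positive index case, so it is not the quantity behind the 12% to 5% hypothesis or the 88% power

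*Combined protocol and SAP*

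**What the plan says.** The stated aim is "To assess the impact of an educational intervention delivered by text messaging on transmission of influenza within households". Under that aim, the Statistical Plan builds the primary outcome in three steps.

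- Index case: "An ill person will be considered an ILI/ARI index case for a household if, at the onset of illness", nobody else in the household had symptoms in the preceding 5 days. No test result is involved.
- Secondary case: "Non-index household members will be defined as secondary cases if they are confirmed by RT-PCR as influenza-positive on day 3 or day 5 swab".
- SAR: the number of "secondary cases of laboratory-confirmed influenza (both symptomatic and asymptomatic) divided by the number of household members minus one (the index case").

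The same section does link contact to index for secondary outcome (3), which counts "any laboratory-confirmed pathogen that is the same as the index case including non-influenza pathogens". The primary outcome has no such link.

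The swabbing rules do not depend on the index result. Under Confirmation of ARI/ILI Symptoms, "Anyone meeting case definition for ARI or ILI will be swabbed". Under Obtaining of Self-Swab Nasal Samples, the plan asks that "everyone else in the household is swabbed 3 and 5 days after the onset of symptoms in the index case". Influenza-positive index households are singled out only in the laboratory section, in a rule for re-testing day-5 samples. That rule does not define an analysis set.

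Sample Size and Power uses 12% versus 5%, 200 households per arm, 3.8 persons per household and an intracluster correlation of 0.29 to reach 88% power. The rates are attributed to the influenza SAR in a cited hand-hygiene trial.

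**The concern.** An SAR for influenza normally describes contacts exposed to an index case who has influenza. The written rule gives the influenza-positive fraction among contacts of anyone with a respiratory illness, most of whom, on the plan's own preliminary data, do not have influenza. Two analysts could follow the aim and the written definition respectively and report primary rates that differ several-fold from the same swabs.

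Two things are at stake. First, the hypothesis and power are stated for one quantity while the definition yields another. Second, the two quantities respond differently to influenza caught outside the household. In the all-index version, such infections among contacts of non-influenza cases add equally to both arms and pull the comparison toward no effect.

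**Working it through.** **Inputs.** Sample Size and Power: 200 households per arm, 3.8 persons (2.8 contacts), ICC 0.29, type I error 5% (taken as two-sided), 12% versus 5%, and an earlier influenza SAR of 16.6% in the team's text-message surveillance study (MoSAIC). Household Transmission of Influenza: SAR at most 19%. Preliminary Studies 3.1: 59.5% of samples positive for any pathogen, and 21.4% of November-March positives were influenza. Preliminary Studies 3.2: 33.3% of swabs positive for influenza.

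**1. Reproduce the stated power.**
- Contacts per arm: 200 × 2.8 = 560.
- Design effect: 1 + (3.8 − 1) × 0.29 = 1.812.
- Effective contacts per arm: 560 / 1.812 = 309.1.
- Two-proportion test with pooled variance, 12% versus 5%: power 87.9%, against 88% stated.
- With 160 households per arm (20% loss): 448 contacts, power 79.9% (80.3% unpooled), against at least 80% stated.

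This method is inferred because it fits. Using 2.8 in the design effect as well (1 + 1.8 × 0.29 = 1.522) gives 92.7%. Either way, every contact in every household carries the 12% or 5% risk. That amounts to one influenza-positive index episode per household.

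**2. What the written SAR would be.** Let f be the share of index illnesses that are influenza and b the influenza positivity among contacts of non-influenza index cases:

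written SAR = f × (SAR given influenza index) + (1 − f) × b

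The first share is f = 0.595 × 0.214 = 12.7%, which assumes that the all-sample 59.5% also holds for November-March. The second is f = 33.3%. Neither is specific to this trial's index illnesses. The documents give no b, so 0 and an assumed 1% are shown.

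| f | b | Control | Education | Ratio |
|---|---|---|---|---|
| 12.7% | 0 | 1.5% | 0.6% | 0.42 |
| 33.3% | 0 | 4.0% | 1.7% | 0.42 |
| 12.7% | 1% | 2.4% | 1.5% | 0.63 |
| 33.3% | 1% | 4.7% | 2.3% | 0.50 |

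**3. Could 12% be the written quantity?** With b = 0, a written SAR of 12% needs an attack rate among contacts of influenza index cases of 0.12 / 0.127 = 94%, or 0.12 / 0.333 = 36%. The documents report 16.6% and at most 19%. So 12% is plausible only as a rate among contacts of influenza-positive index cases.

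**4. Power by number of influenza-positive index episodes.** Same method, one episode per household, 2.8 contacts each:

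| Episodes per arm | 50 | 100 | 150 | 160 | 200 |
|---|---|---|---|---|---|
| Power | 34% | 60% | 77% | 80% | 88% |

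**The case against.** The strongest reply is that the intent is clear. The aim is influenza transmission, the re-test rule singles out influenza-positive index households, and the planning rate is compared with an influenza SAR of 16.6%. That supports reading the gap as an omitted clause, but it does not put the clause into the definition that the analyst will follow.

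A second reply is that the all-index SAR is a legitimate outcome. It compares whole randomized groups, in keeping with the stated intention-to-treat principle, whereas restricting to influenza-positive index cases conditions on a swab taken after randomization by unblinded households. This stands. It is why the all-index SAR should be kept in some form, and why the plan may choose it as primary provided the hypothesis and power are restated. With no background infection it also leaves the rate ratio at 0.42, so the restriction is not needed to protect the relative effect in that case.

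A reader might infer more than the documents support:

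- That the trial is underpowered. Households are followed over several seasons, and the plan gives no expected number of episodes, so 200 per arm may or may not be reached.
- That 12% and 5% also assume a type match between contact and index. The documents do not say so, and the cited trial cannot be checked here.
- That an influenza share below 12.7% applies, from 78 cases among 669 ILI illnesses (11.7%) in Preliminary Studies 2.4. Section 3.2 reports the same study with a 43.6% / 56.4% split by type, which fits 34 and 44 of 78. The 33.3% therefore appears to rest on those same 78 cases, and the 669 appear to include ILI illnesses that were not swabbed.
- That the stated 91% for symptomatic illness (23% versus 11%) is covered too. The method above gives 97.9% there, so that figure must rest on something else, and nothing is concluded about it.

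**Conclusion.** The primary definition is wrong as written, in the sense that it yields a different quantity from the one hypothesised and powered. Read literally, the control-arm SAR would be about 1.5% to 4.0% rather than 12%, given an influenza share of 12.7% to 33.3% and no background infection. Any background infection raises both arms' rates and moves the ratio toward 1 (0.50 to 0.63 at an assumed 1%). The 88% is not an arithmetic error. It rests on an unstated 200 influenza-positive index episodes per arm.

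That the omission exists is plain from the text. That 12% and 5% refer to contacts of influenza-positive index cases is an inference from the arithmetic and from the plan's description of them as an influenza SAR. The sizes depend on shares taken from earlier studies, and the power figures on a method inferred from its fit.

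**What to change.** - In the Statistical Plan, define the primary SAR as the proportion of contacts, in episodes with a PCR influenza-positive index swab, who are PCR influenza-positive on day 3 or day 5.
- State how episodes without a usable index swab are handled. The Missing Data section names contacts' swabs as the main concern and does not mention the index swab, which decides eligibility once the condition is written.
- Keep the SAR over all ILI/ARI index episodes, by randomized arm, as a sensitivity analysis, and report the number of influenza-positive index episodes by arm.
- In Sample Size and Power, restate power by the number of influenza-positive index episodes per arm and give the number expected.
- If the all-index SAR was intended, keep it as primary and restate the hypothesised rates and power for that quantity.
- Optionally, require the same influenza type or subtype as the index. The assay reports these, and secondary outcome (3) already uses a match to the index.

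The cost is SAP wording and a revised power statement. Index and contact swabs are already requested in every episode, so no new data are needed. The restricted set has fewer contacts, and the restated power may be less favourable. It also depends on the index self-swab: in the pilot, 97% of households returned one and its sensitivity for influenza was 87.5%, so some true influenza episodes would drop out. The change does not make up for a shortage of influenza episodes.
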